### **Secondary Endpoint #2/Hypothesis (H2)**

For the secondary hypothesis (H2) , the anti-rotavirus IgA GMTs between participants administered a complete primary infant series of V114 (Group 5) concomitantly with RotaTeqTM versus participants administered a complete primary infant series dosing schedule of Prevnar 13TM (Group 1 + Group 2) concomitantly with RotaTeqTM at 30 days PD3 of V114 or Prevnar 13TM will be assessed via the following non-inferiority hypotheses:

$$H_0: GMT_1/GMT_2 \leq 0.50 \text{ versus}$$
$$H_1: GMT_1/GMT_2 > 0.50$$

Where  $GMT_1$  is the anti-rotavirus IgA GMT for the V114 (Group 5) and  $GMT_2$  is the anti-rotavirus IgA GMT for the Prevnar 13TM (Group 1 + Group 2). A ratio of 0.50 corresponds to a 2.0-fold decrease of anti-rotavirus IgA GMT in the V114 as compared with the Prevnar 13TM. The proposed noninferiority margin of 0.50 for anti-rotavirus responses was chosen based on what was observed in a previous Merck concomitant use study for this

endpoint. The anti-rotavirus IgA responses in the V114 group (Group 5) are non-inferior to the anti-rotavirus IgA responses in the Prevnar 13TM group (Group 1 + Group 2) if the lower bound of the 2-sided 95% CI on the GMT ratio (V114/Prevnar 13TM) >0.50.

The within-group anti-rotavirus IgA GMT along with 2-sided 95% CIs will be computed. Point estimates of anti-rotavirus IgA GMTs are the exponentiated estimates of the mean natural log concentrations. The confidence limits for GMTs are the exponentiated confidence limits for the mean natural log concentrations, based on 1-sample t-distributions. Additionally, anti-rotavirus IgA GMT ratios [V114 (Group 5)/Prevnar 13TM (Group 1 + Group 2)] along with 2-sided 95% CIs will be computed. The 95% CI for the ratio will be calculated using the ANCOVA model utilizing the log-transformed antibody titers as the response with vaccination group and stratification factor (hepatitis B vaccination status before enrollment = Yes, No) as covariates.

For the other secondary endpoints and exploratory continuous descriptive endpoints ;anti-PnPs serotype-specific IgG GMCs at 30 days PD3 of V114 or Prevnar 13TM and prior to Dose 4 and anti-HBsAg GMCs at 30 days PD3, each vaccination groups will be evaluated separately. The point estimates will be calculated by exponentiating the estimates of the mean of the natural log values and the within-group CIs will be derived by exponentiating the CIs of the mean of the natural log values based on the 1-sample t-distribution. For the dichotomous endpoints that immune responses meet threshold value as defined in the objectives , the within-group CIs will be calculated based on the exact method proposed by Clopper and Pearson[Collett, D. 1999].

Reverse Cumulative Distribution Curves for IgG concentrations at 30 days PD3 and 30 days PD4 will be graphically displayed by serotype.

A detailed analysis strategy for immunogenicity endpoints is listed in [Table 6](#).

Table 6 Analysis Strategy for Immunogenicity Variables

Endpoint/Variable (Description, Time Point)	Primary vs. Supportive Approach †	Statistical Method ‡	Analysis Population	Missing Data Approach
Primary Endpoint				
Anti-PnPs IgG GMCs for the 13 shared serotypes contained in V114 and Prevnar 13 TM at 30 days PD4	P	ANCOVA § (estimate, 95% CI)	PP	Missing data will not be imputed
	S		FAS	
Secondary Endpoint #1/Hypothesis (H1)				
Proportion of participants with anti-HBsAg concentration $\geq 10$ mIU/mL at 30 days PD3 of V114 or Prevnar 13 TM	P	Stratified Miettinen and Nurminen ¶ (estimate, 95% CI, p-value)	PP	Missing data will not be imputed
	S		FAS	
Secondary Endpoint #2/Hypothesis (H2)				
Anti-rotavirus IgA GMT at 30 days PD3 of V114 or Prevnar 13 TM	P	ANCOVA § (estimate, 95% CI, p-value)	PP	Missing data will not be imputed
	S		FAS	
Other Secondary Endpoints				
Anti-PnPs IgG GMCs for the 15 serotypes contained in V114 at 30 days PD3	P	Descriptive Statistics (estimate, 95% CI)	PP	Missing data will not be imputed
Proportion of participants with anti-PnPs IgG $\geq 0.35$ $\mu$ g/mL for the 15 serotypes contained in V114 at 30 days PD3	P	Descriptive Statistics (estimate, 95% CI  )	PP	Missing data will not be imputed

† P = Primary approach; S = Supportive approach.

‡ Statistical models are described in further detail below:

§ ANCOVA model with log-transformed antibody responses as response variable and vaccination group, and stratification factor (hepatitis B vaccination status before enrollment = Yes, No) as covariates.

¶ Within group summaries provided using exact method proposed by Clopper and Pearson.

|| Stratification factor (hepatitis B vaccination status before enrollment = Yes, No).

CI = confidence interval; FAS = Full Analysis Set; GMC = Geometric Mean Concentration; GMT = Geometric Mean Titer; HBsAg = Hepatitis B surface antigen; IgA = Immunoglobulin A; IgG = Immunoglobulin G; PD = postdose; PnPs = pneumococcal polysaccharide; PP = Per-Protocol

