

Objectives: To evaluate the anti-PnPs serotype-specific IgG GMCs and the anti-PnPs serotype-specific IgG response rates (proportion of participants meeting serotype-specific IgG threshold value of <math>\geq 0.35</math> <math>\mu</math>g/mL) at 30 days following Dose 3 separately for each vaccination group (Groups 1, 2, 3, 4, and 5).

	

Anti-PnPs serotype-specific IgG responses for the 15 serotypes contained in V114 at 30 days PD3

Objective: To evaluate the anti-PnPs serotype-specific IgG GMCs at 30 days following Dose 4 for participants administered a complete dosing schedule of V114 (Group 5) compared with participants administered a complete dosing schedule of Prevnar 13TM (Group 1).

	

Anti-PnPs serotype-specific IgG responses for the 13 shared serotypes contained in V114 and Prevnar 13TM at 30 days PD4

Tertiary/Exploratory	

Objective: To evaluate the anti-PnPs serotype-specific IgG GMCs prior to Dose 4 separately for each vaccination group (Groups 1, 2, 3, 4, and 5).

	

Anti-PnPs serotype-specific IgG responses for the 15 serotypes contained in V114 prior to Dose 4 (pre-dose 4)

Objective: To evaluate the anti-HBsAg GMCs at 30 days following Dose 3 for participants administered a complete primary infant series dosing schedule of V114 (Group 5) concomitantly with RECOMBIVAX HBTM versus participants administered a complete primary infant series dosing schedule of Prevnar 13TM (Groups 1 and 2) concomitantly with RECOMBIVAX HBTM.

	

Anti-HBsAg response at 30 days PD3 of V114 or Prevnar 13TM

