## 4.2.1 Rationale for Endpoints

### 4.2.1.1 Immunogenicity Endpoints

Previous studies have evaluated the interchangeability of PCVs [Truck, J., et al 2016] [Ciapponi, A., et al 2016]. These studies evaluated the immune responses and reactogenicity in infants primed with Prevnar 13™ and boosted with Synflorix™ (as compared with a Prevnar 13™ booster) and in infants primed with Prevnar™ and boosted with Prevnar 13™. The primary immunogenicity endpoint of these interchangeability studies were assessed 1 month after the administration of the last scheduled dose of the PCVs.

This study will evaluate the safety, tolerability, and immunogenicity of the interchangeability between V114 and Prevnar 13™ in participants administered mixed dosing schedules of Prevnar 13™ and V114 (Groups 2, 3, and 4) compared with participants administered a complete dosing schedule of Prevnar 13™ (Group 1).

Sera from participants will be used to measure vaccine-induced anti-PnPs serotype-specific IgG for the 13 shared serotypes (1, 3, 4, 5, 6A, 6B, 7F, 9V, 14, 18C, 19A, 19F, and 23F) contained in V114 and Prevnar 13™ at 30 days after Dose 4. The primary interchangeability immunogenicity endpoint will be assessed after completion of the full PCV regimen. Anti-PnPs serotype-specific IgG responses will also be measured at 30 days following completion of the primary infant series and prior to Dose 4 to evaluate the anamnestic antibody responses and the persistence of protective immunity.

Sera from participants will also be used to measure anti HBsAg concentration using the hepatitis B enhanced chemiluminescence (ECi) assay. An anti-HBsAg concentration of  $\geq 10$  mIU/mL measured 1 to 3 months after administration of the last dose of the primary 3-dose vaccination series is considered a reliable marker of protection against hepatitis B infection [Van Damme, P. 2016]. In this study, infants will receive a total of 3 hepatitis B vaccinations (2, 4 and 6 months). For those participants who received the first dose of hepatitis B vaccine prior to enrollment in the study, hepatitis B vaccine will be administered at 2 and 6 months of age and not at 4 months. Because antibody responses and GMTs may be slightly higher when hepatitis B vaccination is initiated after 1 month of life [Schillie, S. F. 2013], randomization in this study will be stratified by previous hepatitis B vaccination status before enrollment.

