## **9 STATISTICAL ANALYSIS PLAN**

This section outlines the statistical analysis strategy and procedures for the study. If, after the study has begun, but prior to any unblinding, changes are made to primary and/or secondary hypotheses, or the statistical methods related to those hypotheses, then the protocol will be amended (consistent with ICH Guideline E-9). Changes to exploratory analyses made after the protocol has been finalized, but prior to unblinding, will be documented in a supplemental SAP (sSAP) and referenced in the Clinical Study Report (CSR) for the study. Post hoc exploratory analyses will be clearly identified in the CSR.

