### 9.4.1 Immunogenicity Endpoints

A description of immunogenicity assessments is contained in Section 8.2. Immune responses will be measured for the 13 shared serotypes contained in V114 and Prevnar 13™ (1, 3, 4, 5,

6A, 6B, 7F, 9V, 14, 18C, 19A, 19F, and 23F) or all 15 serotypes contained in V114 (1, 3, 4, 5, 6A, 6B, 7F, 9V, 14, 18C, 19A, 19F, 22F, 23F, and 33F).

The primary immunogenicity analysis endpoint includes:

- Anti-PnPs serotype-specific IgG GMCs for the 13 shared serotypes contained in V114 and Prevnar 13TM at 30 days PD4

The secondary immunogenicity analysis endpoints include:

- Proportion of participants with anti-HBsAg concentration  $\geq 10$  mIU/mL at 30 days PD3 of V114 or Prevnar 13TM
- Anti-rotavirus IgA GMT at 30 days PD3 of V114 or Prevnar 13TM
- Anti-PnPs serotype-specific IgG GMCs for the 15 serotypes contained in V114 at 30 days PD3
- Anti-PnPs serotype-specific IgG response rates (proportion of participants with IgG  $\geq 0.35$   $\mu$ g/mL) for the 15 serotypes contained in V114 at 30 days PD3

The exploratory immunogenicity analysis endpoints include:

- Anti-PnPs serotype-specific IgG GMCs for the 15 serotypes contained in V114 prior to Dose 4
- Anti-HBsAg GMCs at 30 days PD3

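### The exploratory objective compares anti-HBsAg GMCs in Group 5 with Groups 1 and 2, but Section 9.6.1 plans only separate within-group GMCs and no between-group estimate.

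*Combined protocol and SAP*

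**What the plan says.** - **Objective (Section 3, Tertiary/Exploratory).** "To evaluate the anti-HBsAg GMCs at 30 days following Dose 3 for participants administered a complete primary infant series dosing schedule" of V114 (Group 5), given with RECOMBIVAX HB, "versus participants administered a complete primary infant series dosing schedule of Prevnar 13" (Groups 1 and 2), also given with RECOMBIVAX HB.
- **Endpoint (Section 9.4.1).** Listed among the exploratory endpoints as "Anti-HBsAg GMCs at 30 days PD3", with no groups or contrast named.
- **Method (Section 9.6.1, the paragraph after H2).** The endpoint is grouped with the PD3 and pre-dose 4 IgG GMCs: "anti-HBsAg GMCs at 30 days PD3, each vaccination groups will be evaluated separately". The point estimate is the exponentiated mean log value, and the interval is within-group from a one-sample t-distribution.
- **Table 6 and Section 9.1.** Table 6 has rows for the primary endpoint, H1, H2 and two other secondary endpoints, and none for anti-HBsAg GMCs. The SAP summary does not mention the endpoint.
- **Rotavirus comparison, same groups and timepoint (H2, Section 9.6.1).** The ratio Group 5/(Group 1 + Group 2) and its 95% CI come from an ANCOVA "utilizing the log-transformed antibody titers as the response with vaccination group and stratification factor" (hepatitis B vaccination status before enrollment) as covariates. Within-group GMTs are reported as well.

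**The concern.** The objective names two sides and a combined comparator; the method describes five groups one at a time. A statistician following Section 9.6.1 literally would produce five GMCs with intervals, and no estimate or interval for the difference the objective asks about.

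What is at stake is the continuous check for interference between V114 and RECOMBIVAX HB. H1 reduces the same antibody to a yes/no at 10 mIU/mL. When nearly everyone is above that threshold, a fall in concentration shows only partly in the proportion. The GMC ratio is the more sensitive measure of such a fall, although H1 is not blind to it and a large drop would be visible in the per-group GMCs.

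The stratification factor is also left out. Section 4.2.1.1 gives the reason for stratifying: "antibody responses and GMTs may be slightly higher when hepatitis B vaccination is initiated after 1 month of life". Because randomization is stratified on that factor, an unadjusted comparison stays valid; omitting the term costs precision only.

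**Working it through.** **1. Is the comparative wording deliberate?** In Section 3 the objectives for PD3 IgG and pre-dose 4 IgG ask for evaluation separately in each of Groups 1 to 5. The anti-HBsAg GMC objective instead sets Group 5 against Groups 1 and 2. Section 9.6.1 gives all three the same separate-group method, which fits the two IgG objectives and not this one. Being descriptive does not explain the omission: the primary PD4 IgG endpoint is also descriptive and still has ANCOVA ratios with 95% CIs.

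**2. Inputs for the size of the issue.**
- 180 per group (Section 9.9.1) and about 80% evaluable at PD3 (the H1 and H2 power assumptions): 0.80 × 180 = 144 in Group 5 and 0.80 × 360 = 288 in Groups 1 + 2.
- Control rate at ≥10 mIU/mL of 95% and margin of −0.10 (H1 power assumptions).
- SD of log anti-HBsAg: not in the documents. Assumed 1, 1.5 and 2, with log-normal concentrations.

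**3. Reproducing the plan's own figures.** With 144 versus 288, H1 power at 95% versus 95% is 96.3% by Farrington–Manning, and also 96.3% by binomial enumeration with the unstratified Miettinen–Nurminen bound (stated ~96%). H2 power with SD 1.7 and a true ratio of 1 is 97.9% (stated ~98%). With 144 versus 144, both fall to 93.3%. The stated PD3 power therefore relies on pooling Groups 1 and 2, and that pooling is not carried over to the anti-HBsAg GMCs.

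**4. Precision of the missing ratio.** For an observed ratio of 1 the 95% CI is exp(±t × SD × √(1/144 + 1/288)), with t = 1.966 (429 df) and √(1/144 + 1/288) = 0.1021.

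**5. What a true halving would show.** The probability that the CI excludes 1 comes from the noncentral t with noncentrality ln 2/(SD × 0.1021). For H1, the control log-mean is set so that 95% reach 10 mIU/mL, and Group 5 is shifted down by ln 2, so its rate is Φ(1.645 − 0.693/SD).

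| Assumed log SD | 1 | 1.5 | 2 |
|---|---|---|---|
| 95% CI around a ratio of 1 | 0.82–1.22 | 0.74–1.35 | 0.67–1.49 |
| P(CI excludes 1), true ratio 0.5 | >99.9% | 99.5% | 92.3% |
| Implied control GMC, mIU/mL | 52 | 118 | 268 |
| Group 5 rate at ≥10 mIU/mL | 82.9% | 88.2% | 90.3% |
| Difference from 95%, points | −12.1 | −6.8 | −4.7 |
| Miettinen–Nurminen lower bound at expected rates, points | −19.4 | −13.5 | −11.0 |
| P(H1 met) | 0.4% | 14.6% | 38.0% |

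The ratio would show a halved GMC reliably at every assumed SD. H1 would nearly always fail at SD 1, but would be met in more than a third of trials at SD 2.

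**The case against.** - **The endpoint is exploratory and does have a method.** Section 9.6.1 classes it as descriptive and assigns separate summaries; no hypothesis, decision rule or alpha depends on it. That limits the weight. It does not reconcile the method with the objective, and rewording the objective would be the other way to remove the conflict.
- **The missing Table 6 row proves little.** Table 6 omits every exploratory endpoint, including pre-dose 4 IgG GMCs, and Section 9.6.1 opens by limiting itself to primary and secondary objectives. This stands. The stronger evidence is the method paragraph, which does name anti-HBsAg GMCs.
- **H1 already compares the same groups on the same antibody.** It does so at the threshold that Section 4.2.1.1 treats as a marker of protection. Meeting H1 despite a halved GMC is not an error when the loss in the proportion is inside the margin, as it is at SD 1.5 and 2 (6.8 and 4.7 points). The documents set no margin for the hepatitis B GMC, so an interval that excludes 1 has no defined consequence. The comparison in the working shows sensitivity, not a flaw in H1.
- **A crude ratio can be recovered from the planned tables.** Each group's n, GMC and CI give its log mean and standard error, and the CIs in the working are that unadjusted calculation. What is missing is pre-specification and the stratum term, not the data.
- **The H1 figures depend on assumptions.** The 0.4% to 38% spread is mostly the assumed SD, and a single log-normal ignores the two hepatitis B schedules.
- **A supplemental SAP may already fill the gap.** Section 9 allows for one. It is not among the documents, so this cannot be confirmed.

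**Conclusion.** The concern holds and is minor. Section 3 states a between-group objective, and Section 9.6.1 gives a within-group method that does not estimate it. The mismatch is read directly from the text and depends on no assumption; the missing Table 6 row is secondary.

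The figures for its size are illustrative. They rest on log SDs of 1 to 2 that the documents do not supply, log-normal concentrations, a 95% control response and 80% evaluability. Under those assumptions the ratio would be estimated to within a factor of about 1.22 to 1.49 either way, and it could reveal a halving that H1 would pass in up to 38% of trials. No primary or hypothesis-tested conclusion is affected.

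**What to change.** In Section 9.6.1, specify the anti-HBsAg GMC ratio, Group 5/(Group 1 + Group 2), at 30 days PD3 with its 95% CI. Use the H2 ANCOVA: log concentration as response, with vaccination group and hepatitis B vaccination status before enrollment as covariates. Keep the per-group GMCs, label the ratio exploratory and descriptive, and add a row to Table 6. If only within-group description is intended, reword the Section 3 objective to say so; that removes the contradiction but gives up the contrast.

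The cost is a few lines of SAP text, one table row and one model on data already collected, with no effect on alpha or sample size. Section 9 provides the route: "Changes to exploratory analyses made after the protocol has been finalized, but prior to unblinding, will be documented in a supplemental SAP". The change should be made before unblinding.

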## 9.6.2 Statistical Methods for Safety Analyses

Safety and tolerability will be assessed by clinical review of all relevant parameters including AEs and postvaccination temperature measurements. The extended safety follow-up period will occur 6 months following the last dose of vaccination. Safety and tolerability will be

assessed during the entire study period. Primary safety evaluation will be through 14 days post vaccination following any vaccination. Selected safety summaries will be provided for the extended safety follow-up period through the end of the study for each vaccine group.

The analysis of safety results following any vaccination will follow a tiered approach (Table 7). The tiers differ with respect to the analyses that will be performed. AEs (specific terms as well as system organ class terms) are either pre-specified as "Tier 1" endpoints, or will be classified as belonging to "Tier 2" or "Tier 3" based on the number of events observed. The pairwise comparisons for Tier 1 and Tier 2 endpoints include Group 2 vs Group 1; Group 3 vs Group 1; Group 4 vs Group 1; and Group 5 vs Group 1.

Safety analyses will be based on the observed data (ie, with no imputation of missing safety data).

### **Tier 1 Events**

Safety parameters or adverse events of special interest that are identified constitute "Tier 1" safety endpoints that will be subject to inferential testing for statistical significance with p-values and 95% CIs to be provided for between-group differences in the proportion of participants with events; these analyses will be performed using the unstratified M&N method [Miettinen, O. and Nurminen, M. 1985], an unconditional, asymptotic method. For this protocol, solicited injection-site AEs (redness/erythema, swelling, hard lump/induration, and tenderness/pain) from Day 1 through Day 14 postvaccination and solicited systemic AEs (irritability, drowsiness/somnolence, hives or welts/urticaria, and appetite loss/decreased appetite) from Day 1 through Day 14 postvaccination are considered Tier 1 events.

### **Tier 2 Events**

Tier 2 parameters will be assessed via point estimates with 95% CIs provided for differences in the proportion of participants with events (also via the unstratified M&N method) [Miettinen, O. and Nurminen, M. 1985].

Membership in Tier 2 requires that at least 4 participants in any vaccination group exhibit the event. The threshold of at least 4 events was chosen because the 95% CI for the between-group difference in percent incidence will always include zero when vaccination groups of equal size each have less than 4 events and thus would add little to the interpretation of potentially meaningful differences. Because many 95% CIs for Tier 2 events may be provided without adjustment for multiplicity, the CIs should be regarded as a helpful descriptive measure to be used in review, not a formal method for assessing the statistical significance of the between-group differences in adverse events.

In addition to individual events that occur in 4 or more participants in any vaccination group, the broad AE categories consisting of the proportion of participants with any AE, a vaccine-related AE, an SAE, a vaccine-related SAE, discontinuation due to an AE, and the proportion of participants who died will be considered Tier 2 endpoints. The proportion of participants

with maximum temperature measurements meeting the Brighton Collaboration cut points will also be considered Tier 2 endpoints.

### **Tier 3 Events**

Safety endpoints that are not Tier 1 or 2 events are considered Tier 3 events. Only point estimates by vaccination group are provided for Tier 3 safety parameters.

Additionally, solicited AEs may be provided following each vaccination by vaccination group (Groups 1, 2, 3, 4, and 5) in order to better describe the safety of a 4-dose schedule (3 infant primary series + 1 toddler dose) of PCV when switching from Prevnar 13™ to V114 at Doses 2, 3, or 4 during the immunization schedule.

Table 7 Analysis Strategy for Safety Parameters

Safety Tier	Safety Endpoint †	p-Value	95% CI for Between-Group Comparison	Descriptive Statistics
Tier 1	Injection-site redness/erythema (Days 1 to 14)	X	X	X
	Injection-site swelling (Days 1 to 14)	X	X	X
	Injection-site tenderness/pain (Days 1 to 14)	X	X	X
	Injection-site hard lump/induration (Days 1 to 14)	X	X	X
	Irritability (Days 1 to 14)	X	X	X
	Drowsiness/somnolence (Days 1 to 14)	X	X	X
	Hives or welts/urticaria (Days 1 to 14)	X	X	X
	Appetite loss/decreased appetite (Days 1 to 14)	X	X	X
Tier 2	Any AE †		X	X
	Any Vaccine-Related AE †		X	X
	Any SAE †		X	X
	Any Vaccine-Related SAE †		X	X
	Discontinuation due to AE †		X	X
	Death †		X	X
	Maximum temperature measurements meeting the Brighton Collaboration cut points (Days 1 to 7)		X	X
	Specific AEs by SOC and PT ‡ (incidence $\geq 4$ of participants in one of the vaccination groups)		X	X
Tier 3	Specific AEs by SOC and PT ‡ (incidence $< 4$ of participants in all of the vaccination groups)			X

† These endpoints are broad adverse event categories. For example, descriptive statistics for the safety endpoint of “Any AE” will provide the number and percentage of participants with at least one AE.  
‡ Includes only those endpoints not pre-specified as Tier 1 or not already pre-specified as Tier 2 endpoints.

AE = adverse event; CI = confidence interval; PT = preferred term; SAE = serious adverse event; SOC = system organ class; X = results will be provided

